## 5. Study design

### 5.1 Design

This is a 2-arm pragmatic randomized trial among approximately 250 outpatients with advanced cancer to assess response to behavioral nudges to refer to palliative care. The setting will be outpatient oncology at the Ann B. Barshinger Cancer Institute at Lancaster General Health. Eligible clinicians will be randomized in clusters by overlapping clinical team (pod) to receive default EPIC-based prompts for palliative care referral among advanced cancer patients (Arm 1) vs no intervention/usual practice (Arm 2). These nudges have been shown to positively influence clinician behavior and are often used to drive value-based oncology care; however, they have never been studied in the context of palliative care referral. The primary outcome is completion of a palliative care referral within 12 weeks of enrollment.

Following the intervention, brief REDCap questionnaires will be sent to all clinicians who participated in the trial to explore perceptions of the study intervention. This survey should take no longer than five minutes for clinicians to complete and will assess their feedback on the overall intervention in addition to specific components including automated identification of patients, receiving text and email notifications, and identifying the appropriate patients. The survey will also collect basic demographic information (age, gender, practice site, and comfort with SICs) (**Appendix 3**).

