## 9. Analysis plan

We will use REDcap, a HIPAA-compliant and secure database tool, to track all components of the study. Descriptive statistics will be used to estimate the frequencies, means, and standard deviations of the study variables. Differences between study groups in baseline characteristics and clinical outcomes will be assessed with the use of two-sided Fisher's exact tests and chi-square tests for categorical variables and independent-samples Student's t-tests for continuous variables. The unit of analysis will be the patient.

The primary study endpoint is a binary patient-level variable indicating completion of a palliative care visit within 24 weeks of the clinician behavioral nudge. This analysis will be conducted as a time-to-event analysis among all eligible advanced cancer patients. Cox proportional hazard regression analyses, adjusted for baseline covariates, will be used to examine the effect of nudges on completion of palliative care consultation for advanced cancer patients. Competing risk caused by patients who die within 24 weeks will be considered as censored in the analysis. Covariates will include patient and cancer-related variables. Patients will be followed for 24 weeks or until death. Using a longitudinal multilevel mixed-effects model with clustering by discharging clinician (intraclass correlation coefficient 0.5 based on prior randomized trial); a two-sided type I error rate of 0.05; and a baseline palliative care visit rate of 45% (standard deviation 10%), we expect that a sample size of 250 patients will give us 80% power to detect a meaningful 34 percentage point response in palliative care visits, considering the presence of a competing risk of 6-month mortality at 20%.

One secondary outcome will be (1) change in quality of life between 0 and 9 weeks (as measured by the Functional Assessment of Cancer Therapy – General (FACT-G) among patients who receive palliative care compared to matched controls. Multivariate linear regression analyses, adjusted for baseline scores, will be used to examine the effect of palliative care on completion of palliative care consultation for advance cancer patients. For intention-to-treat analyses, we will use the conservative method of carrying the most recent quality-of-life values forward to account for all missing data, including data that are missing owing to death.

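### The primary Cox model censors deaths, so it estimates a cause-specific hazard ratio and not the 24-week visit proportion or the 34-point difference on which the trial is sized

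*Combined protocol and SAP*

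**What the plan says.** Everything that matters here is in one paragraph of Section 9 (Analysis plan).

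- Endpoint: "The primary study endpoint is a binary patient-level variable indicating completion of a palliative care visit within 24 weeks".
- Type of analysis: "This analysis will be conducted as a time-to-event analysis among all eligible advanced cancer patients".
- Model: "Cox proportional hazard regression analyses, adjusted for baseline covariates, will be used to examine the effect of nudges on completion of palliative care consultation".
- Deaths: "Competing risk caused by patients who die within 24 weeks will be considered as censored in the analysis".
- Follow-up: "Patients will be followed for 24 weeks or until death".
- Effect used for power: a "meaningful 34 percentage point response in palliative care visits, considering the presence of a competing risk of 6-month mortality at 20" (per cent), from a baseline visit rate of 45%, with 250 patients and 80% power.

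The same section says in general terms that categorical clinical outcomes will be compared by Fisher's exact and chi-square tests. For deaths in the primary analysis it specifies no cumulative incidence estimator, subdistribution model, binary regression or sensitivity analysis. Kaplan-Meier is named only for overall survival.

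Section 5.1 words the primary outcome differently: "The primary outcome is completion of a palliative care referral within 12 weeks of enrollment". That conflict is a separate matter. This point takes the Section 9 endpoint, which is the one tied to the model and the sample size.

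**The concern.** Three parts of one paragraph sit on different scales: a proportion at 24 weeks, a difference in percentage points, and a hazard ratio among patients who are still alive and have not yet had a visit. The paragraph recognises death as a competing risk, then handles it in a way that removes it from the effect measure.

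For the binary endpoint, a patient who dies without a visit has a known result: no visit. Section 4 presents advanced cancer patients dying without palliative care as the problem that motivates the work. A cause-specific hazard ratio does not register such a death as a failure. It asks only how fast visits occur among those still at risk.

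At stake is whether the primary result can be set against the stated endpoint and the 34 points. There is also a risk at the reporting stage. A reader will want visit rates beside the hazard ratio, and the plan does not say how to produce them when deaths are censored.

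**Working it through.** **Inputs from Section 9.** Control visit rate 45%; effect 34 points, read here as 45% against 79%; 6-month mortality 20%; 250 patients; two-sided 0.05; intraclass correlation 0.5. **Assumptions, not in the plan:** constant hazards over 24 weeks, the same mortality in each arm (varied from 10% to 30%), timing of death independent of timing of visit, and 125 patients per arm.

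**1. The plan's own figure.** Ignoring clustering, 45% against 79% needs 62 patients in total for 80% power, and 250 would give over 99.9%. With the intraclass correlation of 0.5 the design effect is 1 + (m − 1) × 0.5 for m patients per pod. At 36 pods, m = 250/36 = 6.94, the design effect is 3.97, the effective size is 250/3.97 = 62.9 and power is 80.9%. The number of pods is not stated, so the 80% can be neither confirmed nor refuted. What follows does not depend on it.

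**2. Two different quantities.** Let λ be the visit hazard and μ the death hazard per 24 weeks.

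- Proportion with a visit by week 24, deaths counted as no visit: λ/(λ+μ) × (1 − exp(−(λ+μ))).
- One minus Kaplan-Meier with deaths censored: 1 − exp(−λ).
- Cause-specific hazard ratio, the target of the planned Cox model: λ(nudge)/λ(control).

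**3. At 20% mortality.** μ = −ln(0.8) = 0.223. Solving the first expression for 45% and 79% gives λ = 0.685 and 1.915.

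- Check, control: 0.685/0.908 × (1 − exp(−0.908)) = 0.754 × 0.597 = 0.450.
- Check, nudge: 1.915/2.138 × (1 − exp(−2.138)) = 0.896 × 0.882 = 0.790.
- Status at week 24, control: 45.0% visited, 14.7% died unvisited, 40.3% alive unvisited.
- Status at week 24, nudge: 79.0%, 9.2% and 11.8%.
- The deaths censored are about 18 of 125 and 12 of 125.
- Death-censored rates: 1 − exp(−0.685) = 49.6% and 1 − exp(−1.915) = 85.3%, which is 4.6 and 6.3 points too high. Their difference is 35.7 points.
- Cause-specific hazard ratio: 1.915/0.685 = 2.80.

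**4. Range of mortality, true rates held at 45% and 79%.**

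| Mortality per arm | Control, 1 − KM | Nudge, 1 − KM | Difference | Cause-specific HR |
|---|---|---|---|---|
| 10% | 47.2% | 82.1% | 34.9 | 2.69 |
| 20% | 49.6% | 85.3% | 35.7 | 2.80 |
| 30% | 52.4% | 88.6% | 36.2 | 2.92 |

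**5. The hazard ratio does not fix the endpoint result.** With mortality of 25% in control and 15% in the nudge arm, the same 45% against 79% corresponds to a hazard ratio of 2.54. With 15% and 25% it corresponds to 3.08. One result on the stated endpoint can therefore go with quite different values of the planned measure.

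**6. The other reading of the planning figures.** The plan does not say on which scale 45% was measured. If 45% and 79% are themselves death-censored, then λ = −ln(0.55) = 0.598 and −ln(0.21) = 1.561. The proportions with a visit are then 40.8% and 72.8%, a difference of 32.0 points.

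**7. If sicker patients visit sooner.** As an illustration, let 30% of patients have 50% mortality and the rest (0.20 − 0.3 × 0.5)/0.7 = 7%, so that overall mortality stays at 20%. If the sicker group visits two to three times as fast, death-censored rates are 4.0 to 5.3 points too high, but the difference is only 35.0 or 34.5 points. If the other 70% have 20% mortality instead, the rates are about 6 to 8 points too high.

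**The case against.** Censoring competing deaths is the standard way to fit a cause-specific hazard model. Patients who die contribute time at risk until death, and the analysis covers all eligible patients. The endpoint is defined as binary, so a plain proportion with deaths as no visit is available, and the general sentence on Fisher's exact and chi-square tests could produce it. The power statement mentions the competing risk, so mortality was not overlooked.

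Much of this stands, and it rules out several stronger readings that a reader might infer:

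- *That the planned analysis overstates visit rates in both arms.* A Cox model by itself reports no rate. Inflation needs a further step, one minus Kaplan-Meier or a Cox prediction with deaths censored, which the plan does not specify.
- *That patients who die leave the denominator.* They stay in the risk set until they die.
- *That the visit rates given in the plan would fall under a correct analysis.* The only rate given is the 45% planning assumption, and its scale is not stated.
- *That the hazard ratio is wrong by a known amount.* On the cumulative incidence scale at week 24 the matching ratio is ln(0.21)/ln(0.55) = 2.61, against 2.80. These measure different things, so the gap is not an error size.

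What the objection does not remove is the mismatch. The general sentence on categorical tests does not say how deaths are coded, takes no account of randomisation by pod, and does not replace the Cox model as the analysis named for the primary endpoint.

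**Conclusion.** The point holds as a mismatch between the endpoint and the power basis on one side and the named model on the other. It does not show that the model is invalid. The mismatch follows from the text of Section 9 and needs no numerical assumption.

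The size of any inflation is conditional on absolute rates being derived with deaths censored. Under constant hazards and equal mortality of 10% to 30%, it would be about 2 to 7 points in control and 3 to 10 points in the nudge arm. The between-arm difference would move little, from 34 to between 34.9 and 36.2 points. The documents give no mortality by arm and no information on how death relates to visit timing, so these figures show scale and are not predictions.

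This should be corrected before analysis. The remedy is cheap, and without it the primary result cannot be read against the effect for which the trial was sized.

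**What to change.** Replace the censoring sentence in Section 9 with wording to this effect: *The primary estimate is the difference between randomised arms in the 24-week cumulative incidence of a completed palliative care visit. Death without a visit is a competing event. The difference is reported with a 95% confidence interval that accounts for clustering by pod.*

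- Use the Aalen-Johansen estimator, or the binary proportion with deaths before a visit counted as no visit. The two agree when nobody is lost to follow-up alive. If some are, the first handles them.
- Keep the covariate-adjusted Cox model, labelled as a supporting cause-specific analysis, and state that absolute visit rates will not be derived from it with deaths censored.
- Report by arm the numbers visited, died without a visit, and alive without a visit at week 24.
- State whether the 45% and the 34 points count deaths as no visit.
- Define one starting date for both arms. Section 9 counts "completion of a palliative care visit within 24 weeks of the clinician behavioral nudge", and control patients receive no nudge.

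The cost is analysis-plan wording and a little programming. No new data are needed, since dates of visit and death are already required for the planned analyses.

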### *8.2 Procedures*

Baseline data on oncologists and their patients at Lancaster General Health will be obtained from Penn Data Store and Clarity (Epic's data reporting database). Physician data includes demographic information (e.g. sex, type of medical degree, etc.) and may be also obtained from publicly available databases or websites online. Baseline data collected on patients will include age, gender, zip code of residence, type of cancer, Elixhauser comorbidity index, ECOG performance status, whether the patient is on active systemic therapy, and understanding of palliative care. This will be collected via the electronic health record and an in-person enrollment questionnaire (**Appendix D**) upon enrollment into the trial. Those who elect not to participate, but consent to limited data collection, will be asked to fill out a similar questionnaire including reason(s) for not wanting to participate in a de-identified manner (**Appendix E**).

Prior to the trial, staff will randomize each clinician pod in a 1:1 fashion to either intervention or usual care. The Principal Investigator ([name]) will be blinded to arm assignment. In both intervention and control arms, research coordinator staff will identify patients with advanced cancer who are actively cared for within the Ann B. Barshinger Cancer Institute system. They will then regularly review the electronic health record for eligible clinicians to identify patients with an upcoming repeat patient visit who are eligible for palliative care. Patients who are eligible will have a solid malignancy and at least one of the following five conditions: (1) Documented advanced (stage IV) solid malignancy; (2) Known central nervous system metastasis, (3) Eastern Cooperative Oncology Group performance status  $> 2$ , Karnofsky Performance Status  $< 50$ , (4) uncontrolled symptoms such as pain, escalating opioids, nausea/vomiting, distress, dyspnea, delirium, or (5) hospitalization relevant to cancer or treatment.

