For patients whose clinician pods are randomized to the intervention arm, the care team pod will receive an EPIC in-basket message indicating that the patient is eligible for Palliative Care and that a default referral order has been pended for that patient. Clinicians will be given an opportunity to respond if they do not want their patient to be referred to palliative care. For clinicians who do not respond, after the allotted time, the Clinical Research Coordinator will reach out to the patient to introduce palliative care and ask if ABBCI staff can schedule an appointment. For non-English speaking patients, an interpreter will assist research staff. For clinicians who respond no, the pended order will be removed and no patient contact by the research team will occur.

For eligible patients whose clinician pods have been randomized to the control arm, no intervention will be provided. Clinicians will refer patients to palliative care based on their usual practice.

Among patients in the intervention arm for whom palliative care referral is placed, who accept for a scheduler to call them to make an appointment, a trained research coordinator will approach 40

patients as a convenience sample to administer a baseline FACT-G survey (**Appendix A**). 40 randomly selected patients, matched on categories including age category and type of cancer, will be selected from the pods not receiving the intervention. For patients that choose to enroll in the survey component, a baseline FACT-G survey will be administered prior to discharge in-person via paper or electronically. Surveys will be repeated at 3, 6, 9, and 18-week intervals by either telephone or in-person at an in-person visit. For patients that complete the 9-week survey or any survey prior, a \$50 gift card will be given at the 9-week time point. Patients who miss their visits with palliative care will be contacted by the coordinator to identify why (**Appendix F**) and reschedule the appointment.

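### The 80% power is stated for clustering by discharging clinician, but outpatient pods are randomised; with no pod count, size or ICC given, it is unsupported for the randomised design.

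*Combined protocol and SAP*

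**What the plan says.** The only justification of sample size in the supplied text is one sentence in section 9. It assumes a "longitudinal multilevel mixed-effects model with clustering by discharging clinician (intraclass correlation coefficient 0.5 based on prior randomized trial", a two-sided 5% type I error and 20% six-month mortality. It takes "a baseline palliative care visit rate of 45% (standard deviation 10%), we expect that a sample size of 250 patients" and concludes that this "will give us 80% power to detect a meaningful 34 percentage point response in palliative care visits".

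The design sections describe a different cluster. Section 5.1: "Eligible clinicians will be randomized in clusters by overlapping clinical team (pod"; and, of the site, "The setting will be outpatient oncology". Section 8.2: "staff will randomize each clinician pod in a 1:1 fashion to either intervention or usual care". In the intervention arm, "the care team pod will receive an EPIC in-basket message" (section 8.2).

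For the primary analysis, section 9 takes the patient as the unit and says "Cox proportional hazard regression analyses, adjusted for baseline covariates, will be used to examine the effect of nudges". No clustering term is named there.

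**The concern.** In a cluster-randomised trial, power belongs to the unit that is randomised. The power sentence names a clinician, and an inpatient-style one, while the allocation list is made of pods. Section 5.1 places clinicians within pods, so a pod is at least as coarse as a clinician. With an ICC as high as 0.5, extra patients in the same cluster add little information, and power is governed mainly by the number of clusters. That number is not given for either unit.

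Two things are at stake. Readers, above all readers of a null result, will take 80% as the power of the pod-randomised trial. And if the Cox model is fitted as described, its standard errors will ignore the correlation that the power sentence itself regards as large.

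**Working it through.** **Inputs from section 9:** 250 patients, two-sided 0.05, 45% against 45% + 34 points = 79%, ICC 0.5, 20% six-month mortality. **Assumed, because the documents do not give them:** equal clusters split evenly between arms, the numbers of clusters and pods, and the correlations within a pod.

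**1. No clustering.** V = 0.45×0.55 + 0.79×0.21 = 0.2475 + 0.1659 = 0.4134. SE = √(0.4134/125) = 0.0575, and 0.34/0.0575 = 5.91. Power exceeds 99.9%, so the 80% rests entirely on the clustering assumption.

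**2. Reproducing 80% at ICC 0.5.** With K clusters in total and m = 250/K, SE² = V × [ICC + (1 − ICC)/m] / (K/2); t test with K − 2 df. For K = 34, m = 7.35, the bracket is 0.568, SE = √(0.4134×0.568/17) = 0.1175, and 0.34/0.1175 = 2.89. Power is 80.1%. Other formulas reach 80% at 32 clusters (normal test, 80.4%), 36 (normal test with pooled null variance, 80.9%) or 38 (t with pooled null variance, 80.5%). The 80% is attainable, but only with a cluster count that the plan does not state.

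A Cox-based check agrees. HR = ln 0.21/ln 0.55 = 2.61, which needs about 34 independent events. The plan's rates give 125×0.45 + 125×0.79 = 155 events, or about 142 with deaths censored. The allowed design effect is 4.5 or 4.2, that is about 31 or 34 clusters.

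**3. ICC 0.5 applied to whole pods** (formula of step 2):

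| Pods | Bracket | SE | Power |
|---|---|---|---|
| 6 | 0.512 | 0.266 | 17% |
| 10 | 0.520 | 0.207 | 30% |
| 20 | 0.540 | 0.149 | 58% |

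Removing 20% of patients for deaths (N = 200) gives 17%, 30% and 57%, so mortality hardly matters.

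**4. Clinicians at ICC 0.5, grouped in pods.** Take the 34 clinicians of step 2, with c = 34/pods on average per pod and m = 250/34. Let r be the correlation between patients of different clinicians in one pod. The bracket becomes r + (0.5 − r)/c + 0.5/(c·m), with K the number of pods.

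| Pods | Normal test, r = 0 | Normal test, r = 0.05 | t (pods − 2 df), r = 0 | t, r = 0.05 | t, r = 0.10 |
|---|---|---|---|---|---|
| 17 | 82.5% | 79% | 77% | 74% | 70% |
| 12 | 82.5% | 77% | 74% | 68% | 62% |
| 10 | 82.5% | 75% | 72% | 64% | 57% |
| 6 | 82.5% | 68% | 59% | 46% | 38% |

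At r = 0 the variance does not change with grouping, and any fall comes only from the fewer degrees of freedom.

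**5. A small pod ICC.** The plan does not say what the standard deviation of 10% describes. Read as spread between clusters, it implies an ICC of 0.10²/(0.45×0.55) = 0.01/0.2475 = 0.040. The step 2 formula then gives 78% (6 pods), 91% (8) and 96% (10).

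**6. Ignoring pods in the analysis.** The design effect is 1 + (m − 1)×ICC. With 10 pods of 25 it is 13.0 at ICC 0.5 and 1.96 at ICC 0.04. Standard errors that ignore pods would be too small by a factor of about √13.0 = 3.6 or √1.96 = 1.4.

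**The case against.** A reader might infer that the 80% must be too high as soon as a pod holds more than one clinician. The documents do not support that. With no correlation between clinicians in a pod, normal-test power stays at 82.5% for 34 clinicians however they are grouped. The fall to 59–77% comes from a t test on pods − 2 df, which is good practice but which the plan does not specify. With two clinicians per pod the loss is only a few points. The 34 clinicians are themselves solved backwards from 80%. With a pod ICC near 0.04 and 8 or more pods, the 80% would be too low.

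It can also be said that the clinician label is leftover inpatient wording around a calculation done for pods. Sections 8.1 and 8.2 also place the baseline survey before discharge, and if each pod is one clinician's team the mismatch is mainly one of words. That is possible. The plural clinicians and overlapping teams of section 5.1 point the other way without proving it. Nor does the outpatient setting mean that no patient has been discharged, since a cancer-related hospitalisation is one of the qualifying conditions in section 8.2.

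Finally, the multilevel model in the power sentence may signal an intention to allow for clustering in the analysis. The sentence describing the Cox model does not say so.

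What stands is that the unit named for power is not the unit randomised, and the inputs needed to check the 80% for pods are absent from the supplied text.

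**Conclusion.** The 80% is unsupported for the pod-randomised design. The mismatch of units and the missing inputs are plain in the text; the size and direction of any error are not.

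- If the figure was computed for clinicians at ICC 0.5, pod-level power is lower when pods hold several clinicians and either their patients correlate within the pod or a small-sample test on pods is used. For 34 clinicians it runs from about 77% (t test, 17 pods, no pod correlation) to 38% (t test, 6 pods, correlation 0.10).
- If ICC 0.5 belongs to whole pods, fewer than about 32 pods leave the trial short of 80%, and severely so with 6 to 10.
- If the pod ICC is near 0.04, 80% is about right with 6 pods and too low with 8 or more.

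All these figures assume equal clusters, and all pod counts are assumed. No sum in the plan is shown to be wrong. The wording of the model, mixed-effects or Cox, makes little difference to power, but the absence of a pod term in the Cox analysis does affect its standard errors.

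**What to change.** Replace the discharging clinician with the randomised pod, and recalculate from the site's list of pods. The sentence could read: with __ pods per arm, a mean of __ patients per pod (coefficient of variation __), a pod-level ICC of __ on the proportion scale (source __), two-sided alpha 0.05 and pods − 2 df, 250 patients give __% power for 45% against 79%; the difference detectable at 80% power is __ points; 20% mortality enters as __. Define the standard deviation of 10% or delete it, since its obvious reading conflicts with an ICC of 0.5.

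Make the primary Cox model account for pods, for example with a pod frailty term or a pod-robust variance with a small-sample correction.

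The cost is one recalculation and a few rewritten sentences, with no added patients. The stated power may turn out less favourable, and intervals that allow for pods will probably be wider. Restating the power does not raise it; if it falls short, the plan should give the larger difference that the trial can detect.

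### On ordinary readings, the ICC of 0.5 and the 10-point SD in the power statement conflict about twelvefold, and without a cluster count the stated 80% power cannot be reproduced

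*Combined protocol and SAP*

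**What the plan says.** One sentence in Section 9 (Analysis plan) is the whole sample-size justification. It assumes "a two-sided type I error rate of 0.05" and an "intraclass correlation coefficient 0.5 based on prior randomized trial", with "clustering by discharging clinician". It then adds "a baseline palliative care visit rate of 45% (standard deviation 10" per cent) and 20% mortality at 6 months, and concludes that 250 patients give "80% power to detect a meaningful 34 percentage point response in palliative care visits".

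The same section defines the primary endpoint as binary for each patient. Section 8.2 (Procedures) says that staff will "randomize each clinician pod in a 1:1 fashion to either intervention or usual care", and Section 5.1 also describes randomisation by pod.

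The plan does not say what the 10% SD varies over, on what scale the ICC is measured, or how many pods or clinicians take part.

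**The concern.** For a binary outcome the rate, the ICC and the between-cluster SD are tied together: any two fix the third. The power sentence gives all three, and on the usual reading they do not fit. The ICC says clinicians differ enormously in how often their patients see palliative care. The SD says they differ modestly.

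This matters because clustering is what turns a very highly powered comparison into one with 80% power. If the two figures describe the same variation, they imply very different power for the same trial, and a reader of a null result would not know which to judge it against. The level matters too. The ICC is attached to clinicians, but the treatment comparison has only as many independent units as there are pods.

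**Working it through.** **Inputs.** From Section 9: N = 250, two-sided alpha 0.05, control rate 45%, a 34-point effect read as 45% to 79%, ICC 0.5, SD 10%. Allocation by pod, 1:1, is from Section 8.2. The number of clusters k is not in the documents, so I vary it as an assumption, with equal cluster sizes m = 250/k.

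**1. The plan's 80%.** Without clustering, 80% power needs

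n per arm = [1.96 × √(2 × 0.62 × 0.38) + 0.842 × √(0.45 × 0.55 + 0.79 × 0.21)]² / 0.34² = 30.8, so 31.

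Unclustered, 250 patients would give more than 99.9% power for 34 points, and 80% power for about 17.6 points. To bring 250 patients down to 80% for 34 points takes a design effect of 250 / (2 × 30.8) = 4.06.

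With design effect = 1 + (m − 1) × 0.5, m = 1 + 3.06/0.5 = 7.1, and k = 250/7.1 ≈ 35 clusters.

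Other conventions move this only a little:
- separate-variance normal formula: about 32 clusters (28.1 per arm, design effect 4.45, m = 7.9);
- t critical values on k − 2 degrees of freedom: 34;
- events-based Cox calculation with hazard ratio ln(0.21)/ln(0.55) = 2.61: 79% power at 30 clusters;
- N = 200, dropping the 20% expected to die: about 36.

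So ICC 0.5 without the SD reproduces 80% if there are roughly 30 to 35 clusters.

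**2. Do the ICC and SD agree?** On the proportion scale, between-cluster variance = ICC × p(1 − p), and p(1 − p) = 0.45 × 0.55 = 0.2475.
- SD 10 points: ICC = 0.10²/0.2475 = 0.040.
- ICC 0.5: SD = √(0.5 × 0.2475) = 0.352, or 35 points.
- Ratio of ICCs: 0.5/0.0404 ≈ 12.
- Latent logit scale (logistic-normal integration, mean rate held at 45%): SD 10 points gives ICC 0.051, and ICC 0.5 gives an SD of about 30 points. The change of scale does not reconcile them.
- Patient-level SD: √0.2475 = 49.7 points, so 10% cannot be that.

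**3. What each input implies for power.** The table shows power for 45% vs 79% with 250 patients. The first figure is the pooled normal approximation; the second uses t critical values on k − 2 degrees of freedom.

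| Clusters (assumed) | Design effect, ICC 0.5 | Power, ICC 0.5 | Design effect, SD 10 points (ICC 0.040) | Power, SD 10 points |
|---|---|---|---|---|
| 4 | 31.75 | 15% / 10% | 3.48 | 86% / 42% |
| 6 | 21.3 | 21% / 17% | 2.64 | 94% / 78% |
| 8 | 16.1 | 27% / 24% | 2.22 | 97% / 91% |
| 10 | 13.0 | 33% / 30% | 1.97 | 98% / 96% |
| 20 | 6.75 | 57% / 58% | 1.46 | >99% / >99% |
| 35 | 4.07 | 80% / 81% | 1.25 | >99% / >99% |

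The t column uses separate variances, so it can slightly exceed the pooled normal figure when clusters are many. At 10 clusters the separate-variance normal formula gives 37% and 99%. Across 4 to 10 clusters the ranges are therefore about 10% to 37% under ICC 0.5. Under the 10-point SD they are 42% to 96% with t critical values, or 86% to 99% by normal approximation.

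**The case against.** The strongest reply is that the plan never says what the 10% measures. A reader might infer that the two figures can hold together under no interpretation; the text does not support that. The 10% could be uncertainty about the planning rate, variation over time, or the spread of pod averages, and each could coexist with a clinician-level ICC of 0.5. For pod averages it would take about 12 independent clinicians per pod, since 35.2/√12 ≈ 10 points. The documents state none of these meanings and give no pod sizes, so the reply stands as a possibility and does not explain the sentence as written.

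A reader might also infer that the 80% has no basis at all. That goes too far. A calculation for a binary outcome needs the ICC and not the SD, and step 1 recovers 80% from the ICC at a plausible-looking cluster count. Nothing shows that both figures went into the calculation. The 80% is unverifiable rather than shown to be wrong.

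Nor do the documents show that the trial is underpowered, or that it is comfortable under the smaller variance. The low-cluster rows rest on assumed counts. With few pods, even the 10-point SD gives only 42% power at 4 clusters and 78% at 6 once small-sample critical values are used.

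Finally, the endpoint, the randomisation and the sample size need not change, and a null result would be read mainly from its confidence interval. That is fair, but it does not excuse an uncheckable figure as the only power justification.

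**Conclusion.** The point holds in this form: on their ordinary readings the stated ICC and SD conflict by a factor of about 12 on the ICC scale, and the 80% cannot be reproduced from the inputs given. It is reached from ICC 0.5 only with roughly 30 to 35 clusters, and the plan gives no count. It also attaches the clustering to clinicians while randomising pods, and there cannot be more non-overlapping pods than clinicians.

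The conversions in step 2 need only the stated 45% rate and the reading of the 10% as a between-clinician SD. The power figures in step 3 rest further on assumed cluster counts, equal cluster sizes, the same ICC in both arms, and a comparison of proportions in place of the planned Cox model. They show how sensitive the claim is; they are not estimates of this trial's actual power.

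**What to change.** In Section 9:
- Estimate the between-cluster variance of the visit rate once, at pod level, from pre-trial Clarity data (Section 8.2 already names this source).
- State that variance once, as an ICC or an SD, with its level and scale. Delete the 10% SD, or say what it measures.
- State the number of pods and the number of clinicians.
- Restate the power, or the detectable difference, for the planned 250 patients at the level of randomisation. Use small-sample degrees of freedom and a calculation that matches the planned primary analysis.

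The sample size stays at 250. The cost is one data extraction and a rewritten sentence. The downside is that the restated power may be less favourable, and with few pods the variance estimate will itself be imprecise, so power should be shown over a range of values around it.
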